9.6 Gender and Ethnicity

Based on previous data from E1609, the anticipated accrual in subgroups defined by gender and race is:

Ethnic Category	Gender		
	Females	Males	Total
Hispanic or Latino	0	0	0
Not Hispanic or Latino	15	27	42
Ethnic Category: Total of all subjects	15	27	42

Racial Category			
American Indian or Alaskan Native	0	0	0
Asian	0	0	0
Black or African American	0	0	0
Native Hawaiian or other Pacific Islander	0	0	0
White	15	27	42
Racial Category: Total of all subjects	15	27	42

9.7 Imaging Statistical Considerations

9.7.1 3'deoxy-3'-(18)F-fluorothymidine (¹⁸F-FLT) PET/CT

¹⁸F-FLT is a tracer used in PET imaging that measures cellular proliferation in an S-phase-dependent manner. ¹⁸F-FLT PET/CT has been explored in several malignancies, within the first several weeks of treatment, in an effort to predict early response or resistance to therapy. However, in vivo data investigating a role for ¹⁸F-FLT PET/CT in either melanoma, or more generally with MEK or BRAF inhibitor therapy, are sparse. We propose to study the utility of ¹⁸F-FLT PET/CT as an imaging biomarker to guide BRAF/MEK targeted neoadjuvant therapy in melanoma. Demonstrating a significant difference in change in ¹⁸F-FLT PET/CT uptake between patients with and without a pathologic complete response after neoadjuvant therapy, as well as providing data on the diagnostic performance of ¹⁸F-FLT PET/CT uptake in predicting pCR, would yield valuable data toward this end. In addition, demonstrating correlation between the change in ¹⁸F-FLT PET/CT and the change in Ki-67 immunostaining in tumor cells may provide evidence that ¹⁸F-FLT PET/CT is a true imaging measure of proliferation.

9.7.2 Imaging Schedule

All registered subjects are expected to undergo ¹⁸F-FLT PET/CT at the following time points:

- **Baseline FLT-PET/CT:** If the baseline biopsy is done on-study and after registration, then the baseline FLT-PET/CT scan must be performed prior to the baseline biopsy (same day acceptable). The FLT scan needs to be completed within 2 weeks prior to the start of the study-mandated neoadjuvant therapy. If the baseline biopsy of nodal/in transit melanoma was done prior to study enrollment (can be up to 2 months prior), then the baseline FLT-PET/CT scan must be performed within 2 weeks prior to the start of the study-mandated neoadjuvant therapy.
- **Post Neo-adjuvant Imaging:** A FLT-PET/CT scan will be completed after 8 weeks of neoadjuvant therapy and before surgery. **Note:** All neoadjuvant study treatment should be completed prior to post-treatment imaging.
Refer to section [5.3.4](#) for more details on scan timing.

Both ¹⁸F-FLT imaging time points must be scanned on the same qualified PET/CT scanner with imaging technique and parameters to be as close as possible to that of the baseline scan.

NOTE: Institutions getting FLT from outside suppliers should allow time for arranging delivery of FLT.

All ¹⁸F-FLT PET/CT images are to be submitted centrally to ECOG-ACRIN via TRIAD as outlined in Section [4.3.6](#).

It is not expected that the required needle biopsies will have a significant effect upon the ¹⁸F-FLT PET/CT scans. However, the baseline ¹⁸F-FLT PET/CT will be scanned prior to the baseline biopsy,

even if on the same day, to avoid any confounding. The next scheduled biopsy is 2 weeks after initiation of neoadjuvant treatment. The post-neoadjuvant ^{18}F -FLT PET/CT will take place 5-7 weeks after this interim biopsy, and thus is unlikely to be impacted.

9.7.3 Imaging Aims and Statistics

There are four imaging aims, which are secondary to the main trial. All imaging aims will be based on data derived from central review of the acquired ^{18}F -FLT PET/CT scans, and are distinguished into primary and secondary.

9.7.3.1 Primary imaging aim

To compare the change in ^{18}F -FLT PET/CT uptake (from baseline to post-neoadjuvant therapy) among patients with and without pathologic complete response.

The primary imaging aim consists of evaluating whether the anticipated decrease in ^{18}F -FLT PET/CT uptake from the baseline scan to the post-neoadjuvant scan will be greater in pCR versus non-pCR subsets, among patients with clinically resectable or radiographically-detected stage IIIB/C/D melanoma being treated with the neoadjuvant combination of encorafenib (a selective BRAF inhibitor) and binimatinib (a MEK inhibitor).

Distributional summaries of the continuous percent change in ^{18}F -FLT PET/CT SUVmax will be reported, where percent change is defined as $(\text{baseline SUVmax} - \text{post-neoadjuvant SUVmax}) / (\text{baseline SUVmax}) * 100\%$. The comparison of percent change in SUVmax between pCR and non-pCR patients will be performed using a one-sided nonparametric Wilcoxon rank sum test with an alpha level of 0.05.

Of the 42 accrued patients, we assume that 34 (81%) will have interpretable ^{18}F -FLT PET/CT scans at both time points. The mean percentage decrease in SUVmax for non-pCR versus pCR is assumed to be 30% and 50%, respectively, and the standard deviation is assumed to be 20% for both groups. Given that melanoma is expected, on average, to be more proliferative than the breast cancers studied in ACRIN 6688, positing an expected 20% difference in mean percentage decrease in uptake seems justified (55). With a pCR rate of 57%, a sample size of 34 analyzable cases will yield 86% power with a one-sided type I error rate of 0.05 based on the Mann-Whitney Wilcoxon test using Monte Carlo simulation ($n=100,000$) from appropriate null and alternative normal distributions (PASS 2019); however, the power of this comparison varies depending on the pCR rate. For example, it is 84% with a pCR rate as low as 35%, and 83% with a pCR rate as high as 65%.

For the sake of completeness, we will also report distributional summaries and comparisons for percent change in ^{18}F -FLT PET/CT SUVpeak; however, the prespecified primary comparison will be based on ^{18}F -FLT PET/CT SUVmax.

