9.3 Sample Size Considerations and Monitoring Plan

A Simon's optimal two-stage design will be used to allow for an interim analysis for futility. Accrual will be held during the interim analysis. Fifteen (for 14 evaluable) subjects will be enrolled and pCR will be assessed. If 5 or fewer subjects achieve a pCR, the trial will be stopped for futility. If greater than 5 subjects achieve a pCR, then the trial will enroll an additional 27 (for 25 evaluable) patients. If 18 or more subjects out of 39 total evaluable subjects achieve a pCR the study will be considered 'positive'. The study was designed to evaluate the pCR rate improving from 33% to 57%. This design provides 87% power with approximately one-sided type I error rate of 0.05 for the primary endpoint.

The hypothesis states that encorafenib with binimatinib will yield a pCR rate of 57%. The baseline pCR rate of 33% was estimated from published values as summarized in Table 1 in Section [1](#) and is thus the null pCR rate.

We anticipate an average accrual of 1-3 patients per month. The first stage analysis will occur when the first 15 patients have a pCR assessed. Under the null pCR rate of 33%, there is 70% chance of stopping the study after the first stage evaluation. Adverse events will be closely monitored during the study.

Interim safety analyses based on the first 15 patients will evaluate:

- Proportion of patients who develop progressive disease per RECIST 1.1 before surgery but proceed with surgical resection
- Proportion of patients who develop progressive disease per RECIST 1.1 before surgery and are unresectable
- Proportion of patients who develop toxicities that delay or prohibit surgery
- Surgical complications as defined by the operating surgeon as being related to surgery or oral therapy, at any point during follow up

We anticipate that the proportion of patients who experience any of the event listed in i) -iv) will be less than 15%. If at least one patient (out of 15 patients) experiences any of the event listed in i) - iv), the proposed treatment will be considered unsafe and the result will be discussed with the ECOG-ACRIN DSMC. The probability of observing at least one patient with the event in i) ii), iii) or iv) is 0.794 if the true event rate is 10% and is 0.913 if the true event rate is 15%.

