define each holdout subject as test positive ($>$ threshold) vs. test negative (\leq threshold). This step will be repeated until every subject has been a holdout and has test result (positive/negative) defined. Sensitivity and specificity will then be calculated and reported, using the test result for each subject defined during holdout.

The proposed sample size of 42 patients (34 analyzable), assuming a pCR rate of 57%, yields a minimum of 81% power to reject the null hypothesis of an uninformative marker (ROC AUC=0.5) based on a one-sided test with type I error rate of 0.05, assuming the true ROC AUC is 0.74 or higher (PASS 2019).

In addition, estimates of diagnostic performance will be reported for percent change in ^{18}F -FLT PET/CT SUVpeak.

This analysis will be repeated separately for post-neoadjuvant ^{18}F -FLT PET/CT uptake.

Secondary imaging aim #3: To assess the correlation between change in ^{18}F -FLT PET/CT uptake and change in Ki-67.

This secondary imaging aim consists of assessing the correlation between the anticipated decrease in ^{18}F -FLT PET/CT (from the baseline scan to the post-neoadjuvant scan) and the change in tumor cell Ki-67 (from baseline to post-neoadjuvant therapy).

The correlation between percent change in continuous SUVmax and percent change in the continuous Ki67 score will be estimated using the Spearman correlation coefficient. A one-sided correlation test with null hypothesis of zero correlation will be conducted at alpha level of 0.05. The corresponding confidence interval for the estimated Spearman correlation coefficient will also be reported.

The proposed sample size of 42 patients (34 analyzable) yields a minimum of 83% power to detect a nonzero correlation, assuming that the true correlation is 0.5 or higher. A two-sided Spearman correlation test with a type I error rate of 0.05 was used for this computation based Monte Carlo simulation ($n=100,000$) from a bivariate normal distribution (PASS 2019).

Correlation between change in ^{18}F -FLT PET/CT and the early change in tumor cell Ki-67 (from baseline to the week 2 interim biopsy) will also be separately estimated; however, as the week 2 interim biopsy is not mandatory, we expect small numbers of subjects, and thus this analysis will be exploratory. The corresponding correlation with percent change in ^{18}F -FLT PET/CT SUVpeak will also be reported.

10. Specimen Submissions

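### The imaging power figures hold only if the trial passes its futility rule, which section 9.7 does not say; at a 35% pCR rate overall power is about 51-55%, not 84%, even if the test is still run after a stop

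*Combined protocol and SAP*

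**What the plan says.** Section 9.7.3.1 plans to compare percent change in SUVmax between pCR and non-pCR patients "using a one-sided nonparametric Wilcoxon rank sum test with an alpha level of 0.05". Its inputs are:

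- Effect: "The mean percentage decrease in SUVmax for non-pCR versus pCR is assumed to be 30% and 50%, respectively".
- Spread: "the standard deviation is assumed to be 20% for both groups".
- Numbers: of 42 accrued, "we assume that 34 (81%) will have interpretable" scans at both time points.

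On that basis it states 86% power at a pCR rate of 57%. It says power depends on the pCR rate and gives two further values: "it is 84% with a pCR rate as low as 35%, and 83% with a pCR rate as high as 65". Section 9.7.3.2 rests its AUC calculation on the same 42 accrued and 34 analyzable, which it says "yields a minimum of 81% power to reject the null hypothesis of an uninformative marker".

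Section 9.3 enrols 15 patients (for 14 evaluable), holds accrual, and applies this rule: "If 5 or fewer subjects achieve a pCR, the trial will be stopped for futility". The other 27 patients are enrolled only if the rule is passed. Section 9.3 also says: "Under the null pCR rate of 33%, there is 70% chance of stopping the study after the first stage evaluation". Section 9.7 mentions neither the interim stop nor the number of scans available if it happens.

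**The concern.** The 35% figure is offered as a check on how power holds up when the pCR rate is low. But 35% lies just above the 33% null rate at which 9.3 itself expects to stop 70% of the time. At that rate the trial would usually close after 15 patients, with roughly a third of the scan pairs on which the 84% is based. The figure is then the power of a trial that has already continued, not of the design as written.

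The FLT-PET comparison is a prespecified test at the 0.05 level, and section 1.7 calls the imaging endpoint a key secondary endpoint. Readers should be able to tell which power applies to it. Low rates are not remote: section 1.4 cites a pooled pCR rate of 47% for targeted therapy.

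**Working it through.** **Inputs.** From 9.7.3.1: difference 50 - 30 = 20 points, SD 20 (standardised difference 1.0), one-sided Wilcoxon at 0.05, 34 analyzable. From 9.3: 14 evaluable in stage 1, stop at 5 or fewer pCRs. Assumed, because the documents give no figure: stage-1 scan pairs = 0.81 x 15, or about 12, varied from 11 to 14. Ranges below run from the exact test to the normal approximation.

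**1. The plan's own figures.** Simulation with N fixed at 34:

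- 57% (19 v 15): 86-87%; stated 86%.
- 35% (12 v 22): 83.5-84.5%; stated 84%.
- 65% (22 v 12): 83-84%; stated 83%.

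All three reproduce.

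**2. The futility rule.** P(stop) = sum over x = 0 to 5 of C(14,x) p^x (1-p)^(14-x). At p = 0.33 this is 0.699, matching the stated 70%. The full two-stage rule (18 or more of 39) gives type I error 0.048 and power 0.873, matching 9.3. So the rule is read as the plan intends.

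At other rates P(stop) is 0.641 (35%), 0.284 (47%), 0.091 (57%) and 0.024 (65%). Read on 15 patients, it is 0.564 at 35%.

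**3. Overall power.** Power = P(stop) x power given a stop + P(continue) x power given continuation. Each term is averaged over the pCR counts and over which patients have analyzable scans (12 pairs in stage 1, 34 in all).

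- 35%, exact: 0.641 x 0.326 + 0.359 x 0.845 = 0.209 + 0.303 = 0.51.
- 35%, normal approximation: 0.641 x 0.383 + 0.359 x 0.849 = 0.246 + 0.305 = 0.55.
- 57%, exact: 0.091 x 0.367 + 0.909 x 0.846 = 0.033 + 0.769 = 0.80.
- 57%, normal approximation: 0.091 x 0.431 + 0.909 x 0.853 = 0.039 + 0.775 = 0.81 (0.815 unrounded).

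If no test follows a stop, only the second term remains, for example 0.359 x 0.845 = 0.30 at 35%.

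| pCR rate | Stated | P(stop), on 14 | Overall, test run after a stop | Overall, descriptive after a stop |
|---|---|---|---|---|
| 35% | 84% | 0.641 | 51-55% | about 30% |
| 47% | none | 0.284 | 71-74% | about 62% |
| 57% | 86% | 0.091 | 80-82% | 77-78% |
| 65% | 83% | 0.024 | 81-82% | 80-81% |

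**4. Sensitivity at 35%.** With 11 to 14 stage-1 scan pairs, and futility read on 14 or 15, overall power is 49-58% if the test is still run. It is about 30% if not, or 37% with futility read on 15.

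**5. What drives the small gaps.** With 34 cases and the pCR split left to chance, power is about 85% at 57% and 82-83% at 65%. So about 1 point of the gap at 57%, and much of the gap at 65%, comes from the varying split and not from the stop.

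**The case against.** **The figures are not miscalculated.** Section 9.7.3.1 ties its 86% to 34 analyzable cases, and the 35% and 65% values continue that sentence. This stands: what is missing is a stated condition. Powering a secondary aim at full planned accrual is also common practice.

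**The stop is disclosed.** Section 9.3 gives the rule, the accrual hold and the 70% stopping chance, and 9.1 says up to 42 patients. A careful reader can join the two sections. But 9.7 does not do so, and it quotes a power at the very rate where the two pull apart.

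**The 35% may describe the split among 34 completed cases.** This is possible, since a trial that continues can still end near 35%. The text, however, speaks of a pCR rate beside the design rate of 57% and does not limit it to trials that continue.

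**The overall figure is not a single number.** This stands. The stage-1 scan count is not given, nor is what happens to the imaging test after a stop. Section 9.3 speaks both of 14 evaluable and of the first 15 patients assessed. The plan's 70% matches 14 (on 15 it would be 63%), but the range has to be shown.

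**Stronger readings that the documents do not support.**

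- A reader might infer that the 83% Spearman power in 9.7.3.2 is overstated in the same way. That figure was computed two-sided, while the planned test is one-sided. One-sided power is about 89% at 34 cases and about 85% overall at a 57% pCR rate with the stop included, which is above the stated value.
- A reader might infer that the protocol promises a well-powered imaging comparison even if the drug works poorly, or that a null FLT result after a stop would be misread. The text says only that power varies with the pCR rate, and nothing in it shows how such a result would be interpreted.

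**Conclusion.** The point holds as an unstated condition on correct figures. The 86%, 84% and 83% are the power with 34 analyzable cases. At a 35% pCR rate the design gets there only about 36% of the time (1 - 0.641), or 44% if futility is read on 15.

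If the test is still run after a stop, the stated 84% exceeds overall power by about 30 points. The shortfall is about 4-6 points at 57% and 1-2 points at 65%, so it matters only at low pCR rates. These sizes rest on the plan's own effect and SD, about 12 stage-1 scan pairs, and futility read on 14.

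The AUC power in 9.7.3.2 carries the same condition; no overall value is claimed for it here. The sample size, the decision rule and the primary pCR endpoint are unaffected.

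**What to change.** 1. In 9.7.3.1, and for the 34-case AUC power in 9.7.3.2, state that the power figures are conditional on accrual continuing to stage 2.
2. State whether, after a stage-1 stop, the imaging test is still run or the comparison is descriptive only.
3. Give the overall power that matches that choice at 35%, 47%, 57% and 65%, taken from one column of the table only. Figures that count significant tests after a stop cannot stand beside a statement that those comparisons are descriptive.
4. State the assumptions: the expected number of stage-1 scan pairs, and whether futility is read on 14 or 15 patients.

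The cost is wording in the statistical section and less favourable figures at low pCR rates. It needs no extra patients or scans and no change to the two-stage rule.

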9.7.3.2 Secondary imaging aims

Secondary imaging aim #1: To compare post-neoadjuvant ^{18}F -FLT PET/CT uptake among patients with and without pathologic complete response.

This secondary imaging aim will be analyzed in a similar manner to the primary imaging aim, but using post-neoadjuvant ^{18}F -FLT PET/CT SUVmax, as opposed to percent change ^{18}F -FLT PET/CT SUVmax.

Again, for completeness, we will also report distributional summaries and comparisons for post-neoadjuvant ^{18}F -FLT PET/CT SUVpeak.

Secondary imaging aim #2: To estimate an optimal threshold for prediction of pathologic complete response using i. change in ^{18}F -FLT PET/CT uptake, and ii. post-neoadjuvant ^{18}F -FLT PET/CT uptake.

This secondary imaging aim consists of evaluating the diagnostic performance of ^{18}F -FLT PET/CT uptake as a marker of pathologic complete response (pCR), and of estimating the optimal threshold (binary cutpoint) and associated sensitivity/specificity.

Diagnostic performance of percent change in ^{18}F -FLT PET/CT SUVmax (from the baseline scan to the post-neoadjuvant scan) as a marker for pCR status will be assessed using receiver operating characteristic curve (ROC) analysis. In particular, the empirical area under the receiver operating characteristic curve (ROC AUC) will be reported, along with corresponding 95% confidence interval. In addition, we will formally test if the ROC AUC exceeds 0.5 using a one-sided test as suggested by DeLong et al (56) with an alpha level of 0.05. Finally, the optimal threshold (binary cutpoint) of continuous percent change in SUVmax will be estimated by means of the Youden index (57). In order to properly reflect sampling variability, a 95% confidence interval for the optimal threshold will be estimated using the bootstrap technique (58).

The corresponding performance of the optimal threshold (measured via sensitivity and specificity) will be estimated using cross-validation. In particular, we will randomly divide the cohort into 5 folds. Using 4 folds, the ROC curve will be fit and optimal threshold (Youden index) obtained. This threshold derived from the 4 folds will then be applied to the subjects in the remaining holdout fold, in order to

define each holdout subject as test positive ($>$ threshold) vs. test negative (\leq threshold). This step will be repeated until every subject has been a holdout and has test result (positive/negative) defined. Sensitivity and specificity will then be calculated and reported, using the test result for each subject defined during holdout.

The proposed sample size of 42 patients (34 analyzable), assuming a pCR rate of 57%, yields a minimum of 81% power to reject the null hypothesis of an uninformative marker (ROC AUC=0.5) based on a one-sided test with type I error rate of 0.05, assuming the true ROC AUC is 0.74 or higher (PASS 2019).

In addition, estimates of diagnostic performance will be reported for percent change in ^{18}F -FLT PET/CT SUVpeak.

This analysis will be repeated separately for post-neoadjuvant ^{18}F -FLT PET/CT uptake.

Secondary imaging aim #3: To assess the correlation between change in ^{18}F -FLT PET/CT uptake and change in Ki-67.

This secondary imaging aim consists of assessing the correlation between the anticipated decrease in ^{18}F -FLT PET/CT (from the baseline scan to the post-neoadjuvant scan) and the change in tumor cell Ki-67 (from baseline to post-neoadjuvant therapy).

The correlation between percent change in continuous SUVmax and percent change in the continuous Ki67 score will be estimated using the Spearman correlation coefficient. A one-sided correlation test with null hypothesis of zero correlation will be conducted at alpha level of 0.05. The corresponding confidence interval for the estimated Spearman correlation coefficient will also be reported.

The proposed sample size of 42 patients (34 analyzable) yields a minimum of 83% power to detect a nonzero correlation, assuming that the true correlation is 0.5 or higher. A two-sided Spearman correlation test with a type I error rate of 0.05 was used for this computation based Monte Carlo simulation ($n=100,000$) from a bivariate normal distribution (PASS 2019).

Correlation between change in ^{18}F -FLT PET/CT and the early change in tumor cell Ki-67 (from baseline to the week 2 interim biopsy) will also be separately estimated; however, as the week 2 interim biopsy is not mandatory, we expect small numbers of subjects, and thus this analysis will be exploratory. The corresponding correlation with percent change in ^{18}F -FLT PET/CT SUVpeak will also be reported.

10. Specimen Submissions

Representative tumor tissue from the involved lymph node (not a primary melanoma) (block preferred) and related pathology reports from a procedure performed within two (2) months prior to the performance of imaging and from the surgical resection after eight (8) weeks of treatment must be submitted for central diagnostic review. Additional tumor tissue and peripheral blood specimens are to be collected and submitted per patient consent.

- Additional tumor tissue from the archived pre-trial biopsy and surgical biopsy
- Tumor tissue from research biopsies performed prior to start of treatment, if performed, and after two (2) weeks (+/- 1 week) off treatment
- Peripheral blood specimens for potential future research studies

All specimens must be clearly labeled with the ECOG-ACRIN protocol number [EA6183], the patient's initials and ECOG-ACRIN patient sequence number, the collection date, and specimen type. For pathology materials, it is strongly recommended that full patient names be provided.

It is required that all specimens submitted on this trial be entered and tracked via the ECOG-ACRIN Sample Tracking System (STS) (Section [10.4](#)). An STS shipping manifest form is to be included with every submission.

If you have any questions concerning tumor tissue and peripheral blood submissions or need information regarding potential alternative submission requirements, please contact the ECOG-ACRIN CBPF at [contact] or [contact].

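### Sensitivity and specificity of the FLT-PET threshold rest on one random 5-fold split of about 34 patients; averaging over repeated splits would remove avoidable noise at almost no cost

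*Combined protocol and SAP*

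**What the plan says.** Section 9.7.3.2, secondary imaging aim #2, estimates an optimal cutpoint for percent change in SUVmax as a marker of pCR, with its sensitivity and specificity. For those two measures the plan states "we will randomly divide the cohort into 5 folds". The training step is "Using 4 folds, the ROC curve will be fit and optimal threshold (Youden index) obtained", and that cutpoint classifies the patients in the remaining fold. The stopping rule is "This step will be repeated until every subject has been a holdout and has test result (positive/negative) defined", so each patient is held out once. The result is then reported: "Sensitivity and specificity will then be calculated and reported, using the test result for each subject defined during holdout".

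The text mentions no repeated partitions, averaging, stratification by pCR or seed, and no interval for sensitivity or specificity. The bootstrap interval in the same section is for the threshold. The analysis is to be repeated for post-neoadjuvant uptake.

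**The concern.** Five folds of 34 patients means four folds of 7 and one of 6, so each threshold is fitted on 27 or 28 patients. A Youden cutpoint from so few observations can move noticeably when a handful of patients change folds. Two analysts who follow the text exactly on the same locked data can therefore report different sensitivity and specificity, and the plan does not say which answer counts.

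At stake are two descriptive estimates for percent change, and the same two for post-neoadjuvant uptake. The split adds noise that comes from the computation rather than from the patients. It also leaves room, with no bad intent needed, for a seed to be kept or changed after the result is seen.

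**Working it through.** **Inputs.** Section 9.7.3.1: "we assume that 34 (81%) will have interpretable" scans at both time points; the mean percentage decrease in SUVmax "for non-pCR versus pCR is assumed to be 30% and 50%, respectively"; SD 20% in both groups. Section 9.7.3.2: "assuming a pCR rate of 57%, yields a minimum of 81% power" if the true AUC is 0.74 or higher, one-sided alpha 0.05. Group sizes: 0.57 × 34 = 19.4, taken as 19 pCR and 15 non-pCR.

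**Reproducing the plan's figures.** The plan gives no precision figure for the cross-validated measures, so the marker model was checked against its power statements.
- Implied AUC = Φ((50 − 30)/(20√2)) = Φ(0.707) = 0.76, close to the stated 0.74.
- AUC power with the Hanley-McNeil variance [A(1−A) + (n1−1)(Q1−A²) + (n0−1)(Q2−A²)]/(n1·n0), where Q1 = A/(2−A) and Q2 = 2A²/(1+A). At A = 0.74: (0.1924 + 18 × 0.0397 + 14 × 0.0818)/285 = 0.00720, SE 0.0849. At A = 0.5: (0.25 + 18 × 0.0833 + 14 × 0.0833)/285 = 0.01023, SE 0.1012. Power = Φ((0.24 − 1.645 × 0.1012)/0.0849) = Φ(0.867) = 80.7%. The Obuchowski variance gives 81.4% and a simulated DeLong test 82.9%. The plan states 81%.
- Simulated Wilcoxon power is 86.0%, 83.9% and 83.3% at splits of 19/15, 12/22 and 22/12. The plan states 86%, 84% and 83% for pCR rates of 57%, 35% and 65%.

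**Effect of the split alone.** Data were simulated from these inputs (250 data sets). The plan's procedure was run on 200 random partitions of each, with the patient data held fixed.
- SD across splits: median 5.3 points for sensitivity and 6.2 for specificity; root mean square 5.9 and 6.8.
- Scale: one patient is 1/19 = 5.3 points of sensitivity or 1/15 = 6.7 points of specificity.
- Two seeds differ by at least 10 points in sensitivity 27% of the time, in specificity 24%, and in at least one of them 44%.
- On one data set built from normal quantiles, the central 95% of splits ran from 0.47 to 0.68 for sensitivity and from 0.47 to 0.73 for specificity.
- Stratifying the folds by pCR leaves an SD of about 5 to 6 points at AUC 0.74. With AUC 0.86 the SD is still about 4 to 5 points.

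**Against sampling error.** Across data sets, the total SD of a single-pass estimate is about 14.5 points (sensitivity) and 14.0 (specificity). Averaging over splits brings these to about 13.2 and 12.3. Variance removed: 1 − (13.2/14.5)² = 17% and 1 − (12.3/14.0)² = 23%. Separate runs put the averaged SD between about 12 and 14.5 points, so 13 to 14 is a fair round value.

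**Effect of repetition.** The seed SD of a mean over R partitions is the single-split SD divided by √R. With R = 500: 5.9/√500 = 0.26 and 6.8/√500 = 0.30 points.

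**The case against.** The strongest reply is about proportion. The seed SD is about one patient changing sides, against sampling error more than twice as large. Single-pass 5-fold cross-validation is a recognised method, and by scoring held-out patients the plan already guards against judging a Youden cutpoint on the data that chose it. No test, success criterion or treatment decision depends on these two values, and section 9.7.3 makes all imaging aims secondary to the main trial. A fixed seed would make the result reproducible. All of this stands, and it is why the point is minor.

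It does not rescue the single split. A fixed seed makes the answer repeatable but still arbitrary. Averaging estimates the same quantity with less variance and needs no further patients.

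A reader might infer that the seed is the main source of error, or that the whole aim is unreliable. The documents do not support either. The aim is stated as estimating a threshold, with sensitivity and specificity as associated measures, and its formal test and power statement concern the AUC. The empirical AUC, the DeLong test and the full-cohort threshold use no fold split, and the bootstrap interval for the threshold uses its own resampling.

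**Conclusion.** The point holds as a small, nearly free improvement. As written, the plan does not fix its own sensitivity and specificity: on the same data the split moves them with an SD of about 5 to 6 and 6 to 7 points, and two seeds disagree by 10 points or more on at least one measure about 44% of the time. Averaging removes nearly all of that and about 17% to 23% of total variance.

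It would be wrong to conclude that repetition makes the estimates precise: an SD of about 13 to 14 points remains because there are only about 34 patients. The primary imaging comparison and the pCR endpoint are untouched. The figures assume normal data with equal SDs, as in the plan's power calculation, and 34 analysable patients at a 57% pCR rate. The documents give no patient-level distribution against which to test this.

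**What to change.** In section 9.7.3.2, replace the single division with repeated 5-fold cross-validation, for example 500 random partitions with a prespecified seed, and report the mean sensitivity and specificity over repeats. Apply this to percent change and to post-neoadjuvant uptake. Stratifying the folds by pCR is preferable but is the lesser part, since it leaves most of the seed noise if used alone.

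An interval for sensitivity and specificity would be useful because sampling error dominates. If it is obtained by bootstrap, resample patients and keep all copies of a patient in the same fold. Otherwise duplicates fall in both training and holdout sets and bring back the optimism that cross-validation is meant to remove.

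The cost is a short text change, slightly longer if an interval is specified, and minutes of computing. There is no change to sample size, data collection or patient procedures. The one small loss is that there is no longer a single 2x2 table of holdout calls.
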